## 6.3. Secondary analyses

The primary analysis (i.e. mixed effects repeated measures model including every teacher who has at least one measure of the outcome i.e. at baseline, one or two year follow up) will be repeated with a treatment by time interaction term added to the model. This will allow estimation of treatment effect at 12 and 24 month follow ups separately. Analysis of secondary outcomes will include linear, ordinal and logistic regression models dependent on the nature of the outcome variable being analysed (continuous, ordinal or binary respectively).

For secondary individual level outcomes that are measured at baseline, 12 and 24 months (e.g. PHQ-8), repeated measures models will be used, these models will include random effects for clustering by individual (due to repeated measure) and by school. All individuals with at least one observation of the outcome measure will be included in the model for that outcome measure using maximum likelihood under a Missing at Random (MAR) assumption. For each secondary individual level outcome that are measured at baseline, 12 and 24 months, 3 models will be presented:

- Model 1: Unadjusted model Repeated measures of the outcome regressed on treatment arm accounting for clustering due to repeated measures and by school (using random effects).
- Model 2: Partially adjusted model Model 1 plus adjustment for stratification variables.
- Model 3: Fully adjusted model Model 2 plus additional adjustment for covariates. For teacher based outcomes the covariates adjusted for will be sex and years of experience, for student based outcomes sex and ethnicity will be included as covariates.

For each secondary individual level outcome measured only at baseline and 24 months, 3 models will be presented:

- Model 1: Unadjusted model Outcome at 24 months regressed on treatment arm and baseline value of the outcome, accounting for clustering by school (using a random effect).
- Model 2: Partially adjusted model Model 1 plus adjustment for stratification variables.
- Model 3: Fully adjusted model Model 2 plus additional adjustment for covariates. For teacher based outcomes the covariates adjusted for will be sex and years of experience, for student based outcomes sex and ethnicity will be included as covariates.

For each secondary school level outcome measured only at baseline and 24 months, 2 models will be presented:

- Model 1: Unadjusted model Outcome at 24 months regressed on treatment arm and baseline value of the outcome (no need for any adjustment for clustering).
- Model 2: Adjusted model Model 1 plus adjustment for stratification variables.

## 6.4. Sensitivity analysis

The sensitivity of the results to the assumptions about the missing data will be assessed using multiple imputation for missing outcome data. This will include imputing under a range of assumptions about the missing data mechanism – allowing the missing data mechanism to depend on the unobserved outcome data, the arm of the trial, and both. We will assess the impact of non-response and missing data on teacher WEMWBS and PHQ-8 outcomes and student WEMWBS and SDQ outcomes. The sensitivity of conclusions to late returned questionnaires will also be checked, by repeating the analyses with only those questionnaires returned within 2 days of the initial data collection date. We will also re-run the primary analyses without identified outliers, as well as those without major protocol violation to assess the effect of outliers and protocol violation on the main outcome.

#### 6.5. Subgroup analysis

The effect of the intervention on teacher WEMWBS and PHQ-8 score at follow-up will be tested for interaction with: baseline wellbeing / depression score (grouped as above or below the bottom quartile of the WEMWBS, or with a score of 10 or more on the PHQ-8), geographical area (Wales / England), school-level FSM and gender of teacher. The effect of the intervention on student WEMWBS and SDQ score at follow-up will be tested for interaction with baseline wellbeing / SDQ score (grouped as above or below the bottom quartile of the WEMWBS and a score of 16 or more on the SDQ), geographical area, school and individual level FSM, gender and ethnicity. Results will be interpreted with caution due to the low power and number of interactions being tested.

We will use a Complier Average Causal Effect (CACE) approach (using Instrumental Variable analysis or Principal Stratification) [7] to examine the impact of MHFA training on follow up WEMWBS and PHQ-8 scores, comparing those who completed the 1 or 2 days training in the intervention schools with those in the control schools who would have completed the training, had they been offered it. This will be based on matching their gender, role in the school and years of experience with those who were trained. For each participant we will calculate a summary score of the two outcomes, and use the summary score to account for the repeated measurements (thus reducing the 2 measures to a single measure) and, if only a single measure is available then we will use just the single measure. We will include robust standard errors to account for clustering at the school level.

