#### 2.7. Sample size and justification

The primary outcome measure will be the WEMWBS scale. A change of 3 points on this scale is close to the difference in mean scores between the highest and lowest ranked schools in the pilot study. The sample size takes account of clustering; in the pilot data from 6 schools, the WEMWBS ICC (calculated using the loneway command in Stata) for teachers was 0.01 (95%Cl 0.00, 0.05) [1]. We assume a mean of 50 teachers followed up per school after allowance for 20% dropout (with a coefficient of variation of sample size of 0.5), and an SD for WEMWBS of 8.4 (based on the pilot data). Given that estimates based on pilot data can be unreliable [2], assuming an ICC of 0.05, which is greater than that seen in the pilot, -a sample size of 24 schools (12 intervention and 12 control) would achieve over 80% power. This would rise to 98% if the ICC is 0.02, and fall to 68% for an ICC of 0.08. These estimates of power are likely to be conservative given that the sample size calculation does not account for the baseline assessment of the outcome.

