## 2.10. Outcome measures

## 2.10.1. Primary outcome

The primary outcome is the average effect of the intervention on mental wellbeing of teachers over the duration of follow up, measured using the self-completed WEMWBS questionnaire [4] collected at baseline, one and two year follow ups. The WEMWBS scales from 14-70 and will be analysed as a continuous variable.

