## 2.10.2. Secondary outcomes

Time averaged treatment effects will be reported for those variables collected at baseline, one and two year follow ups:

- Teacher depression measured by PHQ-8 [5] that scales from 0 to 24
- Teacher presenteeism measured by WPAI [6], that scales from 0 to 10
- Teacher absence (ever/never in the past 4 weeks) and total number of days of absence, which will be collected at baseline, one and two years follow up by self-report

Adjusted difference between trial arms at 2 years follow up will be reported for those variables collected only at baseline and two year follow up:

- Student mental wellbeing measured by the WEMWBS
- Student psychological distress, measured by the SDQ [7] that scales from 0 to 40
- Teacher absence collected from schools' routine data sources
- Teacher retirement/resignation collected from schools' routine data sources
- Student attendance (%) for all year groups

Year 11 attainment (percentage achieving five or more grades 5-9 GSCEs including English and Maths)

Teacher PHQ-8 and student WEMWBS and SDQ will be measured as continuous variables. PHQ-8 will also be measured as an ordinal variable (a score of 0-4 indicating no depressive symptoms / 5-10 indicating mild symptoms / 10-14 indicating moderate symptoms / 15-19 indicating moderately severe symptoms 20-24 indicating severe) and a binary variable, with a cut-point of 10 or more indicating depression. Teacher absence and presenteeism will be treated as binary (any vs no absence in the previous four working weeks and health problems having 0 effect vs 1-10 effect on work over the previous four working weeks) to ascertain the impact of the intervention on any absence or presenteeism. Teacher absence will also be categorised as 0 / 1 day or less / 2 -7 days / more than 7 days, and the categories for teacher presenteeism will be 0 / 1-5 / 6-10. Teacher absence and teacher retirements/resignations as reported by schools, student attendance and

student attainment (% students achieving five or more 5-9 grade GCSEs including English and Maths) will all be reported at a school level and will be treated as continuous variables.

	Baseline	Year 1	Year 2
Teacher	WEMWBS	WEMWBS	WEMWBS
	PHQ-8	
 
PHQ-8
 
	• PHQ-8
	Presenteeism	Presenteeism	Presenteeism
	• Teacher absence (past 28	Teacher absence	Teacher absence (past 28
	days)	(past 28 days)	days)
Student	- WEMWBS		- WEMWBS
	- SDQ		- SDQ
School	- Teacher absence (%)		- Teacher absence (%)

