## 8.8. Subgroup analysis

 Table 11. Subgroup analysis results

	I vs $C^{\dagger}$ adjusted difference in	Bonferroni p-value
Baseline WEMWBS*	means (95% CI)	(adjusted difference)
Geographical location		
School level FSM		
Gender		
I= intervention; C= cont	rol.	
Binary outcome indic	ating grouped as above bottor	n quantile of the WEMW
Teachers PHQ-8 score		
with following		
interactions:		
	I vs C † adjusted difference in means (95% CI)	Bonferroni p-value (adjusted difference)
Baseline PHQ-8*		
Geographical location		
School level FSM		
Gender		
I = intervention; C = cont	rol.	
Binary outcome indic	ating a score of 10 or more on	the PHQ-8
Student WEMWBS score with following interactions:		
	I vs C † adjusted difference in means (95% CI)	Bonferroni p-value (adjusted difference)
		(
Baseline WEMWBS * Geographical location Individual FSM School FSM Gender		
Baseline WEMWBS * Geographical location Individual FSM School FSM Gender † I= intervention; C= cont * Binary outcome indic	rol. ating grouped as above bottor	n quartile of the WEMW
Baseline WEMWBS * Geographical location Individual FSM School FSM Gender † I= intervention; C= cont † Binary outcome indic Student SDQ score with following interactions:	rol. ating grouped as above bottor	n quartile of the WEMW
Baseline WEMWBS * Geographical location Individual FSM School FSM Gender † I= intervention; C= cont † Binary outcome indic Student SDQ score with following interactions:	rol. ating grouped as above bottor I vs C † adjusted difference in means (95% CI)	n quartile of the WEMW Bonferroni p-value (adjusted difference)
Baseline WEMWBS * Geographical location Individual FSM School FSM Gender † I= intervention; C= cont * Binary outcome indic Student SDQ score with following interactions: Baseline SDQ *	rol. ating grouped as above bottor I vs C † adjusted difference in means (95% CI)	n quartile of the WEMW Bonferroni p-value (adjusted difference)

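### Section 6.5 tests moderation by baseline mental health only on split scores; if moderation is roughly linear, the WEMWBS quartile split loses about 46% of the information.

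*SAP*

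**What the plan says.** SAP 2.1.2 asks, as a secondary objective, whether any effects differ by individual baseline mental health, among other factors. Section 6.5 carries this out with interaction tests. For teacher outcomes the baseline score enters "grouped as above or below the bottom quartile of the WEMWBS, or with a score of 10 or more on the PHQ-8". For student outcomes it enters "grouped as above or below the bottom quartile of the WEMWBS and a score of 16 or more on the SDQ". Table 11 in section 8.8 describes the baseline WEMWBS and PHQ-8 moderators as binary and reports Bonferroni p-values.

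As outcomes, the same scores are kept whole. Section 2.10.1 says of the teacher measure: "The WEMWBS scales from 14-70 and will be analysed as a continuous variable". Section 2.10.2 says: "Teacher PHQ-8 and student WEMWBS and SDQ will be measured as continuous variables". PHQ-8 is also analysed there in ordinal and binary form.

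No interaction between arm and a continuous baseline score appears in the SAP. The sensitivity analyses in 6.4 do not include one, and the moderators in 6.6 are other variables (stress, satisfaction, support, relationships and the like). On the subgroup tests as a whole, 6.5 says: "Results will be interpreted with caution due to the low power and number of interactions being tested".

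**The concern.** Splitting a score treats everyone on one side of the cut as alike. A teacher just above the bottom quartile counts the same as one at the top of the scale. If the effect rises or falls steadily with baseline wellbeing, much of the evidence for that trend lies within the two groups, and the split test cannot use it.

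The SAP already accepts that these tests are weak, and Table 11 corrects them for multiplicity. Part of the weakness comes from the coding and could be avoided with the data already being collected. At stake is a wrong impression that the effect does not vary with baseline mental health, on a question the trial set out to answer. The main comparison is not at stake.

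**Working it through.** **1. The SAP's own power figures.** The SAP gives none for the interaction tests, so the only check possible is on the main effect. Inputs from section 2.7: a difference of 3 points ("A change of 3 points on this scale is close to the difference in mean scores"), "an SD for WEMWBS of 8.4 (based on the pilot data"), 12 schools per arm, mean 50 teachers followed up per school, coefficient of variation of cluster size 0.5. Two-sided 5% is assumed, in line with the 95% interval in 6.2.

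- Design effect = 1 + ((0.5² + 1) × 50 − 1) × ICC = 1 + 61.5 × ICC. At ICC 0.05 this is 4.075.
- Non-centrality = 3 / (8.4 × √(2 × 4.075 / 600)) = 3 / 0.979 = 3.06.
- On a t distribution with 22 degrees of freedom, power is 83.4% (SAP: over 80%). The same steps give 97.7% at ICC 0.02 (SAP: 98%) and 68.1% at ICC 0.08 (SAP: 68%).

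The sample size section reproduces and is not part of this point.

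**2. Information kept by a split.** With linear moderation, the efficiency of a split moderator relative to the whole score is the squared correlation between the indicator and the score. For a normal score with a fraction p on one side of the cut, this is φ(z_p)² / (p(1 − p)).

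WEMWBS bottom quartile, p = 0.25: φ(−0.674) = 0.318, so the efficiency is 0.318² / 0.1875 = 0.539. About 46% is lost. The split test needs 1 / 0.539 = 1.86 times the sample for the same power.

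**3. Effect on power.** Power after the split = Φ(δ√0.539 − 1.96), where δ is the expected z value of the continuous test and √0.539 = 0.734.

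| Continuous test | δ | After quartile split |
|---|---|---|
| 90% | 3.24 | Φ(0.42) = 66% |
| 80% | 2.80 | Φ(0.10) = 54% |
| 50% | 1.96 | Φ(−0.52) = 30% |

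The starting powers are illustrations, because the SAP states none.

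**4. Simulation of the same contrast.** Assumptions: 1,200 people (24 × 50), no clustering, normal baseline score, linear moderation. The continuous test had 74.5% power. The split test had 47.8% with the continuous score kept as main effect (efficiency 0.54) and 41.2% if the main effect is split too (efficiency 0.45). Section 6.5 does not say which of these main effects is meant.

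**5. PHQ-8 at 10 and SDQ at 16.** The SAP gives no baseline distribution, so these figures are a range over assumptions.

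| Assumed shape | Share at or above the cut | Information lost |
|---|---|---|
| Normal | 10% | 66% |
| Normal | 15% | 57% |
| Normal | 20% | 51% |
| Normal | 30% | 42% |
| Skewed (gamma), PHQ-8 | 9% to 25% | 42% to 34% |
| Skewed (gamma), SDQ | 15% to 29% | 43% to 36% |

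From an 80% start, a 66% loss leaves 37% power (Φ(2.80 × √0.342 − 1.96)). A 34% loss leaves 63% (Φ(2.80 × √0.663 − 1.96)).

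**6. The opposite case.** The simulation was repeated with an effect that steps only at the quartile. The linear test then had 39% power, and the split test 55% (split main effect) or 65% (continuous main effect).

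**The case against.** The strongest reply is that the loss is conditional. It assumes a roughly linear change, and step 6 shows that a true step at the cut reverses the ranking. A step is not far-fetched: peer support and mental health first aid are meant for people in difficulty, and benefit could concentrate there. The SAP supports neither shape over the other. This stands, and it rules out a plain swap to a linear term with nothing else.

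The PHQ-8 cut is also not arbitrary. Section 2.10.2 defines 10 or more as indicating depression and uses it as a binary outcome. Whether the effect differs in that group is a coherent prespecified question, so the group is worth keeping.

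Third, 6.5 already promises caution, and Table 11 gives 95% confidence intervals, so an imprecise null would be visible. That limits the harm, but caution does not recover information the coding has removed.

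Two stronger readings are tempting, and the document does not support them:

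- A reader might infer that about half the information is lost for all three scores. Only the WEMWBS figure follows from the stated cut, and even that needs a near-normal score and linear moderation. The PHQ-8 and SDQ figures depend on distributions the SAP does not give.
- A reader might infer that the WEMWBS cut is meaningless because it depends on who responded. Section 6.5 does not say whose distribution defines the quartile, and a lowest-wellbeing group can be interpreted in any case. If an external distribution were meant, the share below the cut need not be 25%.

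**Conclusion.** The point holds in conditional form. The SAP answers a stated secondary question only through split scores and plans no continuous interaction. Under roughly linear moderation of an approximately normal score, with a quarter of the sample below the cut, the WEMWBS split loses about 46% of the information, and 80% power falls to about 54%. For PHQ-8 and SDQ the loss is roughly one third to two thirds over the shapes and prevalences assumed here. The simulation ignored clustering, so its power values are illustrative.

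The planned tests are valid and contradict nothing else in the SAP. This is an avoidable loss of power in a secondary analysis that can be repaired cheaply. It should be made, but it has no bearing on the primary result.

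**What to change.** In section 6.5:

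- Prespecify arm by continuous baseline score as the interaction test for WEMWBS, PHQ-8 and SDQ.
- Prespecify a non-linearity check, for example a quadratic or spline term and its interaction with arm.
- State that the test is fitted to follow-up outcomes with baseline as a covariate. In the primary model (6.2) baseline is itself one of the repeated outcomes, so its role as a moderator has to be settled. The grouped version has the same gap.
- Keep the quartile, PHQ-8 and SDQ groups in Table 11 to present effects with 95% confidence intervals, and say whose distribution defines the WEMWBS quartile.

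The cost is SAP wording and a short model specification, with no new data. The continuous test takes the place of the split test, so the number of main interaction tests does not grow. It should be written in before the results are seen, because section 1 places analyses not specified in advance outside the plan. The downside is lower power than the split if the effect truly changes only at the cut; the non-linearity check and the retained groups would help to show that.

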## 2.5. Description of interventions

Each intervention school will receive the following:

- Staff peer support service: 8 % of staff who are nominated via confidential voting of questionnaire respondents will be selected (ensuring a mixture of gender and years of experience and (non)teaching role) and will receive 2 day MHFA training. Then will act as peer supporters to other staff members.
- INSET teacher training using MHFA for schools and colleges: Another 8 % of teachers only (targeted at tutors or heads of year) who did not receive the 2 day MHFA training, will receive one day youth MHFA course. The learning will be applied during usual interactions with students.
- Mental health awareness raising session: One hour training for all teachers, during in-service training or meeting time, that will introduce the intervention and focus on the importance of mental health issues in school.

Control schools will continue with usual practice.

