## **3. GENERAL ANALYSIS CONSIDERATIONS**

## 3.1. Analysis datasets

Full Analysis set: All teachers who are in post and all students in the appropriate year group who are on the register, in the randomised schools, during at least one of baseline, one or two year data collection, will form the main analysis sample. It is analysis of this sample which is in accordance with the "intention to treat" (ITT) principle.

Per protocol set: All participants in the Full Analysis set who are from schools with no major protocol violations that could interfere with the objectives of the study.

ITT will be used as primary outcome, then as sensitivity we will use ITT and impute missing data, and we will also present per protocol analysis, as well as CACE analysis.

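### Section 6.5 allows an instrumental-variable CACE of individual MHFA training, although the intervention is designed to reach untrained teachers as well

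*SAP*

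**What the plan says.** Section 6.5 states: "We will use a Complier Average Causal Effect (CACE) approach (using Instrumental Variable analysis or Principal Stratification"). The stated aim is "to examine the impact of MHFA training on follow up WEMWBS and PHQ-8 scores", so the exposure is a teacher's own completion of a one- or two-day course. The contrast is described as "comparing those who completed the 1 or 2 days training in the intervention schools with those in the control schools who would have completed" such a course if offered. Those control teachers are to be identified as follows: "This will be based on matching their gender, role in the school and years of experience with those who were trained". The paragraph then covers combining the two follow-up scores and using robust standard errors. It does not choose between the two estimators, state their assumptions, say whether an IV would use all teachers or a matched subset, or mention adjustment for baseline score.

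Section 3.1 commits to reporting the result: "we will also present per protocol analysis, as well as CACE analysis".

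Section 2.5 describes three components:

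- Peer supporters, who take the two-day course: "8 % of staff who are nominated via confidential voting of questionnaire respondents will be selected". Their role is then set out: "Then will act as peer supporters to other staff members".
- A separate 8% of teachers, mainly tutors or heads of year, who take the one-day course.
- An awareness session: "One hour training for all teachers".

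**The concern.** With school allocation as the instrument, IV attributes the whole difference between arms to the teachers who were trained. That is valid only if allocation changes nothing for untrained teachers (the exclusion restriction). In this trial an effect on untrained colleagues is the purpose of the peer support service, and every teacher is offered the awareness session. The restriction therefore fails by design, and the SAP neither states nor defends it.

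The other routes that section 6.5 leaves open have a different problem. A comparison of trained teachers with would-be-trained controls captures everything the intervention did for those teachers, including the school-wide part, yet the section labels it the impact of training. It also depends on finding the right control teachers. Two-day trainees were chosen by colleagues' votes, and votes are not among the matching variables.

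What is at stake is a secondary causal claim about training that could be several times too large, or that could mix training, school-wide effect and selection, with the choice of estimator still open.

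**Working it through.** **1. The plan's own figures.** The SAP gives no figure for the CACE. The 3 points and SD 8.4 used below come from section 2.7, so I checked them against its power statement. The design effect is 1 + ((1 + 0.5²) × 50 − 1) × ICC = 1 + 61.5 × ICC, and the effective n per arm is 600 / design effect. With a two-sided 5% test (assumed) and a noncentral t on 22 df, the results are:

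| ICC | Design effect | Effective n per arm | Power | SAP |
|---|---|---|---|---|
| 0.02 | 2.230 | 269.1 | 97.7% | 98% |
| 0.05 | 4.075 | 147.2 | 83.4% | over 80% |
| 0.08 | 5.920 | 101.4 | 68.1% | 68% |

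The figures reproduce.

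**2. Share trained.** Section 2.5 gives 8% on the two-day course plus a further, non-overlapping 8% on the one-day course, so p = 0.16. This assumes full uptake, and that 8% of staff equals 8% of analysed teachers. Section 2.5 lets non-teaching staff be peer supporters, while section 2.4 excludes them from the analysis. I take 12-20% as an assumed range, with no training in control schools (also assumed).

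**3. What an all-teacher IV estimates.** Let d be the school-wide effect on every teacher and t the extra effect of being trained.

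- ITT = d + p × t
- IV = ITT / p = t + d/p
- Multiplier on d = 1/p: 1/0.12 = 8.3; 1/0.16 = 6.25; 1/0.20 = 5.0

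**4. Worked cases at p = 0.16**, with a simulation of 24 schools × 50 teachers (ICC 0.05, 2,000 runs each). In the last column the would-be-trained controls are known without error and do not differ in prognosis.

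| d | t | ITT | IV = ITT/0.16 | d + t | Simulated IV mean | Simulated mean, trained v. true would-be trained |
|---|---|---|---|---|---|---|
| 0 | 2 | 0.32 | 2.00 | 2 | 1.97 | 2.02 |
| 1 | 0 | 1.00 | 6.25 | 1 | 6.47 | 1.06 |
| 1 | 2 | 1.32 | 8.25 | 3 | 8.41 | 2.99 |
| 3 | 0 | 3.00 | 18.75 | 3 | 19.15 | 3.03 |

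Row 1: with no school-wide effect the IV is right, so the error comes only from breaking the restriction. Row 2: training adds nothing, yet the IV reports about 6 points where the direct contrast reports about 1. Row 4 is the extreme case in which the full 3 points are school-wide; 18.75 points is 18.75/8.4 = 2.2 SD. Row 3: even the ideal direct contrast returns d + t = 3, not the training effect of 2.

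**5. An IV within a matched subset.** If 80-90% of that subset took the training (assumed), the multiplier on d is 1/0.80 = 1.25 to 1/0.90 = 1.11.

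**6. Matching variables against selection rules.** Section 6.5 matches on gender, role and years of experience.

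- One-day trainees are targeted by role, so matching on role is informative for them.
- Two-day trainees are picked from those nominated by colleagues, with gender, experience and role deliberately spread. Those variables therefore say little about who was nominated, and the votes themselves are not matched on.
- Baseline WEMWBS and PHQ-8 are collected (section 2.10.2), but the CACE paragraph does not use them.

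**The case against.** The strongest reply is that the SAP never commits to an all-teacher IV. It names principal stratification as an alternative, and the contrast it spells out, trained teachers against matched control teachers, does not divide an ITT effect by 0.16. A reader might infer that the planned CACE as a whole treats training as the only route of effect and inflates the result six-fold. The text does not support that. The multiplier belongs to one permitted option, applies only to the school-wide component, and is close to 1 in a matched subset with high uptake. The 18.75-point case is likewise a limit: it needs the whole 3 points from the sample-size section to be school-wide.

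It can also be said that the three matching variables are the ones section 2.5 names when describing selection, so matching does achieve something. That is fair for role among one-day trainees. It leaves nomination and baseline score uncontrolled.

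Finally, this is a supplementary analysis, and the results tables in section 8 have no CACE row. That limits the consequence, but section 3.1 still says the analysis will be presented.

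What remains is that one of the two named estimators contradicts section 2.5, no assumptions are stated, and on the same data the open choice can give answers about six-fold apart (6.47 against 1.06 in row 2 of the worked cases).

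**Conclusion.** The point holds in a conditional form. The IV option in section 6.5 relies on an exclusion restriction that the intervention is designed to break. If it is run over all teachers, any school-wide effect is multiplied by about 6: 6.25 at 16% trained, and 5 to 8.3 for an assumed 12-20%. These figures rest on full uptake, on 8% of staff being 8% of analysed teachers, and on no training in control schools. They say nothing about how large the school-wide effect will be.

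Principal stratification without the restriction, and the matched comparison, escape the multiplication but estimate d + t under the label of training. The matched comparison is also open to selection bias of unknown size and direction. The primary intention-to-treat analysis in section 6.2 is unaffected, so this should be corrected but does not threaten the trial's main result.

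**What to change.** In section 6.5:

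- Delete the teacher-level IV option.
- Define the estimand as the total effect of the whole intervention in teachers who would be trained, not the effect of training alone. If principal stratification is kept, state that it is fitted without the exclusion restriction and list the assumptions that replace it.
- Adjust the comparison for baseline WEMWBS or PHQ-8, as appropriate to the outcome, and for peer nominations made before allocation if they exist in both arms. The SAP does not say whether they do.
- Label the result, here and in section 3.1, as an observational, supplementary comparison.

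Do not substitute a school-level CACE at the delivery thresholds in section 6.6 (8% trained, 75% at the awareness session). It needs the same restriction for schools below the threshold, and a school just short of it has still been exposed.

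The cost is SAP wording, with no new data collection. The downside is that training is no longer isolated as a separate causal effect.

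### The matched CACE comparison in SAP 6.5 leaves out baseline WEMWBS and PHQ-8, so part of any baseline wellbeing gap between trainees and their matched controls would be read as an effect of training

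*SAP*

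**What the plan says.** SAP 6.5 describes a CACE analysis of MHFA training on follow-up WEMWBS and PHQ-8, "using Instrumental Variable analysis or Principal Stratification". Teachers who completed the one-day or two-day course in intervention schools are set against "those in the control schools who would have completed the training, had they been offered it". The rule for finding those control teachers follows: "This will be based on matching their gender, role in the school and years of experience with those who were trained". The repeated measures are reduced to one number: "For each participant we will calculate a summary score of the two outcomes". Standard errors are robust to clustering by school. No baseline score appears in this description.

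SAP 2.5 explains how people come to be trained. For the two-day course, "8 % of staff who are nominated via confidential voting of questionnaire respondents will be selected", with attention to a mixture of gender, experience and teaching or non-teaching role. The one-day course goes to "Another 8 % of teachers only (targeted at tutors or heads of year) who did not receive the 2 day MHFA training".

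Baseline data exist: SAP 2.10.1 has teacher WEMWBS "collected at baseline, one and two year follow ups", and the schedule in 2.10.2 shows the same for PHQ-8.

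**The concern.** Once the comparison is limited to people who were selected for training and completed it, randomisation no longer guarantees that the two sides are alike. The matching then has to make them alike. Gender, role and years of experience do not measure whether colleagues would have voted for someone, or whether that person would have completed the course. Both may be related to the teacher's own wellbeing before training.

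The variable that would absorb most of such a difference is the baseline value of the outcome, and the SAP uses it elsewhere. Section 6.3 adjusts for the baseline value when an outcome is measured only at baseline and 24 months. Section 6.6 adjusts the mechanism measures for baseline. The subgroup paragraph of 6.5 itself groups teachers by baseline score. The trainee contrast needs baseline more than these do and states none. Section 6.6 also warns of confounding in the mechanism analysis, while 6.5 gives no such warning for the CACE. At stake is whether a difference between trainees and matched controls can be read as an effect of training.

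**Working it through.** **The plan's own figures.** The CACE text states no figure. The one design figure in the SAP is the power in 2.7, which confirms the inputs borrowed below: difference 3, SD 8.4, 50 teachers per school, CV 0.5, 12 schools per arm. Two-sided 0.05 is assumed. The design effect at ICC 0.05 is 1 + ((1 + 0.5²) × 50 − 1) × 0.05 = 4.075. The standard error is 8.4 × √(2 × 4.075 / 600) = 0.98. A non-central t with 22 degrees of freedom gives 83.4%. ICC 0.02 and 0.08 give 97.7% and 68.1%. The SAP's over 80%, 98% and 68% are reproduced.

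**Bias of a follow-up-only matched contrast.** With no true effect, expected difference = baseline gap × slope of follow-up on baseline. The slope equals the correlation r if baseline and summary score have the same SD. The SAP gives neither gap nor slope. Assumed here: gap 1 to 3 points (1/8.4 = 0.12 SD to 3/8.4 = 0.36 SD) and r 0.5 to 0.7.

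**Precision.** Trainees followed up: 16% × 50 × 12 = 96, treating both 8% groups as shares of teachers. That is 8 per school, so the design effect is 1 + 7 × ICC.
- ICC 0.01: 8.4 × √(2 × 1.07 / 96) = 1.25
- ICC 0.05: 8.4 × √(2 × 1.35 / 96) = 1.41

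| Assumed gap | Bias (r 0.5 to 0.7) | Share of 3 points | False-positive rate, nominal 5% |
|---|---|---|---|
| 1 | 0.5 to 0.7 | 17% to 23% | 6.5% to 8.6% |
| 2 | 1.0 to 1.4 | 33% to 47% | 11% to 20% |
| 3 | 1.5 to 2.1 | 50% to 70% | 19% to 39% |

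**Simulation.** Each setting had 400 simulated trials with a true effect of zero. Half the trainees were picked with a lean toward higher baseline wellbeing, and comparators were picked without regard to wellbeing.
- Gap about 1.9 to 2.0: false effect 0.97 (r 0.5) and 1.30 (r 0.7).
- Gap about 3.4: false effect 1.66 and 2.35.
- Same comparison with baseline WEMWBS as covariate: −0.05 to 0.02 across all settings, including those with no built-in lean. The SD of the estimate fell from about 1.4 to between 0.9 and 1.1.
- Arm difference divided by 0.16, the simple instrumental-variable estimate: means between −0.29 and 0.46. With an SD of about 5.6 the simulation error is 5.6/√400 = 0.28, so these are compatible with zero.

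Baseline adjustment removes the bias completely here because selection was built to depend on baseline wellbeing alone. Selection on unmeasured traits would remain.

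**The case against.** The strongest objection is that 6.5 names two recognised CACE methods. An instrumental-variable estimate uses the randomised arm and needs no matched comparators, so a gap between trainees and look-alike controls does not enter it. Under principal stratification, the three variables might only be predictors of compliance. This stands, and a reader who infers that the CACE is biased under every estimator goes beyond the document. But the SAP chooses neither method, does not say how matching feeds into either, and states that the comparison rests on matching. Instrumental variables also have a condition of their own: allocation must not affect untrained teachers, who in 2.5 receive the one-hour session and have access to peer supporters.

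It can also be said that the three variables are close to the selection attributes 2.5 names, and that role addresses the targeting of tutors and heads of year. That is fair for the one-day group. It does not cover votes or completion.

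The size is assumed throughout, and a gap near zero is possible. The upper end is demanding: if role matching removed the gap among one-day trainees and the two groups were equal in size, an average of 3 points would need voted trainees to differ by 6 points (6/8.4 = 0.71 SD). The groups are only roughly equal, since one 8% is of staff and the other of teachers.

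**Conclusion.** The point holds for the matched comparison as written: it is non-randomised and leaves out baseline scores that the trial collects. The part of a baseline gap that passes through is the gap times the slope, illustrated as 0.5 to 2.1 points on assumptions the SAP neither supports nor rules out. No corresponding figure was worked out for PHQ-8.

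Three stronger readings are tempting and not supported:
- That the whole of any gap becomes a training effect. Only the carried-over share does.
- That the estimate will favour training because nominated teachers are better off or volunteer. The SAP does not say that trainees volunteer, nor how they compare at baseline, so the direction is unknown.
- That the trial's main result is in doubt. The CACE is a supporting analysis listed in 3.1 after the ITT analysis, with no row of its own in the section 8 tables, and the primary estimate, test and sample size do not depend on it.

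This is a cheap improvement.

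**What to change.** In SAP 6.5:
- Add baseline WEMWBS and PHQ-8 to the matching or compliance-prediction variables, and adjust each summary score for its own baseline value.
- State which estimator will be used and how matching enters it.
- Handle missing baseline scores by the imputation already foreseen in 3.2, or report how many teachers are lost.
- Add nomination votes only if they were collected in both arms before allocation; the SAP does not show whether they were.
- Label any matched result as a non-randomised comparison.

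The cost is SAP wording and a little more analysis of data already collected. Without imputation, teachers lacking a baseline score drop out. The full analysis set in 3.1 admits teachers present at any one of the three time points, and the SAP gives no figure for late joiners or baseline non-response, so that loss cannot be sized in advance.
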